## 7.2 Secondary and Tertiary Outcomes

### 7.2.1 To examine how mental health is impacted by the provision of a Service Dog versus an Emotional Support Dog.

Mental health will be examined using the PCL-5 total score, C-SSRS based suicidality, the PHQ-9 total score, and the seven components and the total score of the PSQI. To begin the analyses, the distribution of each variable will be examined for outliers and to determine if transformations (to normalize data) are necessary. The mean and standard deviation of PCL-5 total scores, PHQ-9 total scores, PSQI seven component scores and the PSQI total score will be calculated for each time point. The number and percentage of participants reporting suicidality will also be reported for each time point. Data will be presented in two ways: 1) for all participants paired and 2) by treatment group.

Secondary continuous variable analyses will include linear repeated mixed model analysis on PTSD Symptom Severity using PCL-5, depression, sleep and thoughts of suicide. Any variable considered to be a potential confounder will be included in the model. Suicidality will be examined using logistic regression methods.

Open-ended questions are asked in the Dog Related Questionnaire. The purpose of these questions is to gain further information about the human-animal bond that occurs for Veterans who have PTSD and are paired with a Service Dog or Emotional Support Dog. The questions will be entered as text-based fields into the database. The categorized responses to these questions will help guide future planning needs, if a program is implemented.

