The International Conference on Harmonization (ICH) defines adverse events (AEs) for Clinical Safety Data Management (ICH-E2A) as “any untoward medical occurrence in a clinical investigation subject that is subjected to one of the study treatments that do not necessarily have to have a causal relationship with the treatments. An AE, therefore, can be any unfavorable or unintended sign (including an abnormal laboratory finding), symptom, or disease temporally associated with the study interventions.”

For the purposes of this study, the study interventions are: a) being paired with a Service Dog and b) being paired with an Emotional Support Dog.

In this study, information on AEs related to or possibly related to study intervention for the participant, participant family members, or the study dog, and on all serious adverse events (SAEs) will be collected and recorded. See the section below on “Relatedness”. A separate section below describes the collection of safety information for SAEs.

The reporting period for AEs begins when the participant signs the informed consent form and continues until 30 days after: the participant’s completion, early termination of study participation, or the end of the study (whichever comes earlier). Each related/possibly related AE will be reported to the Sponsor, the VA Cooperative Studies Program, including any increase in frequency or severity of a condition that was present prior to the start of the study. During the study, adverse events can be spontaneously reported or elicited during open-ended questioning, examination, or evaluation of the participant at study visits.

Related or possibly related adverse events not meeting the criteria for an SAE (see below) must be recorded on the Adverse Event Form. (Those that meet SAE criteria are documented on the SAE Form.) One form should be completed for each AE reported. Adverse events should be reported in sequential order as they occur and submitted with the other case report forms for the participant's visit.

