#### **2.3.4 Columbia Suicide Severity Rating Scale (C-SSRS)**

The C-SSRS is a 4-page form asking questions about suicidal ideation, intensity of ideation, and suicidal behavior. Developed by Posner and collaborators at the New York State Psychiatric Institute (Oquendo et al 2003), the scale is intended for use by trained administrators. The questions contained in the C-SSRS are suggested probes. Ultimately, the determination of the presence of suicidality depends on clinical judgment.

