### 3.3.2 Exclusion Criteria

- 1) Hospitalization for mental health reasons in the past 6 months

- Once six months since hospitalization have passed, the individual may become eligible to participate in the study
- 2) Aggressive behavior that would make it unsafe for dog
- 3) Diagnosis of psychosis, delusions, dementia, moderate or severe alcohol/substance disorder (SUD), or moderate to severe traumatic brain injury as determined by the presence or absence of a condition following scoring of MINI responses or as documented in chart notes.  
SUD assessment (alcohol/non-alcohol):
  - Ineligibility is based on the presence of a Moderate (4-5 symptoms) to Severe (6+ symptoms) SUD as identified by the MINI within the previous 12-month period starting from date of the study MINI screening.
  - If a Moderate to Severe SUD has been documented or communicated by the referring clinician or potential participant, or is noted in the EMR prior to the initial MINI screening visit, individuals should be scheduled for their initial screening visit on a timeline commensurate with meeting the 12-month SUDs eligibility window.
  - If an individual is identified as ineligible during the initial screening visit (i.e. MINI SUDs score  $\geq 4$ ) he/she may be re-evaluated later at the discretion of the study team. Re-evaluations should be scheduled based on a timeline commensurate with meeting the 12-month SUDs eligibility window (absence of a Moderate to Severe SUD for the previous 12 months). If at re-evaluation the individual has  $< 4$  symptoms, he/she may become eligible to participate in the study.
- 4) Active suicidal intent as determined by a CPRS flag for suicidal intent or an endorsement of yes to question 5 (active suicidal ideation with specific plan and intent) on the C-SSRS completed at the Clinic Qualifying Visit.
  - An endorsement of yes to question 4 (Active Suicidal Ideation with Some Intent to Act, without Specific Plan) without endorsement of question 5 indicates that the individual needs additional assessment to determine eligibility.
- 5) Homicidal intent or cognitive disabilities that would preclude safety of dog and/or ability to participate in the study.
- 6) Social, mental or physical condition that prevents the individual from either giving informed consent or participating in the study.
- 7) Participation in another unapproved research trial.

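### No planned C-SSRS output shows severe ideation or suicidal behaviour by arm over the whole post-pairing period, and the SAP leaves both C-SSRS outcomes undefined

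*SAP*

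**What the plan says.** SAP 2.3.4 describes the instrument: "The C-SSRS is a 4-page form asking questions about suicidal ideation, intensity of ideation, and suicidal behavior". It gives no items, cut-off, grade or category for an analysis variable, and leaves the presence of suicidality to clinical judgment. The neighbouring sections are more definite: PCL-5 and PHQ-9 scoring is described, and the PSQI has a full algorithm in Appendix 2.

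SAP 7.2.1 then plans three uses of the C-SSRS:

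- A descriptive summary: "The number and percentage of participants reporting suicidality will also be reported for each time point". On layout: "Data will be presented in two ways: 1) for all participants paired and 2) by treatment group".
- A model for a continuous outcome: "Secondary continuous variable analyses will include linear repeated mixed model analysis on PTSD Symptom Severity using PCL-5, depression, sleep and thoughts of suicide". No score for thoughts of suicide is defined.
- A model for the yes/no outcome: "Suicidality will be examined using logistic regression methods". How repeated visits are handled is not stated.

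At entry the plan does use grades. SAP 3.3.2 excludes on "endorsement of yes to question 5 (active suicidal ideation with specific plan and intent", while a yes to question 4 without question 5 leads to further assessment.

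On safety, Protocol section XIII says: "Related or possibly related adverse events not meeting the criteria for an SAE (see below) must be recorded on the Adverse Event Form". All SAEs are collected whatever their cause. SAP 8 tabulates AEs and SAEs by arm and MedDRA term and does not mention the C-SSRS.

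**The concern.** The form separates kinds and grades of suicidality, and the plan relies on that separation to decide who may enter. After pairing, no planned table keeps it. A reader of the results could not learn how many Veterans in each arm ever reached question 4 or 5 ideation, ever showed suicidal behaviour, or became worse than before pairing.

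This matters for two reasons. Hypothesis 2b claims a reduction in suicidal thoughts, and the protocol's publication plan includes a paper on suicide intent. Also, once the envelope is opened (SAP 3.4), neither site staff nor the Veteran is blind. If the definition is not fixed in advance, it may be chosen with the arms known. A visit percentage that is level between arms, or falls over time, could then be read as reassurance about severe suicidality that it does not provide.

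**Working it through.** The plan gives no C-SSRS rate, power or sample size to reproduce. The check is a comparison of sections, with arithmetic only to show how the percentages behave.

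**1. Collected against reported.**

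| Recorded on form 11 (SAP 2.3.4) | Used at entry (SAP 3.3.2) | Planned post-pairing output (SAP 7.2.1, 8) |
|---|---|---|
| Ideation, questions 4 and 5 | Yes, treated differently | No table by grade |
| Intensity of ideation | Not named | None |
| Suicidal behaviour | Not named | No separate table |
| Worst grade, ever/never, shift | Not applicable | None |

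SAP Table 2 requires form 11 at months 3, 6, 9, 12, 15 and 18. The descriptive output is therefore six separate percentages per arm, with no summary across them.

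**2. What one yes/no can carry.** It has a single cut. Set at any ideation, it merges mild with severe. Set at question 4 or 5, it loses the milder ideation that belongs to Hypothesis 2b. If behaviour also counts, ideation and behaviour cannot be told apart. Assumed counts show the first case: with 22 of 110 Veterans flagged in each arm, both show 22/110 = 20.0%, whether the severe cases among them number 2 or 8.

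**3. What a visit percentage does when Veterans leave.** Protocol section XVIII gives 82 per arm and a 25% loss: 82/0.75 = 109.3, rounded up to 110. With 110 paired and 25% lost, 110 × 0.75 = 82.5 are seen at month 18. Assume 2 and 8 severe cases per arm, each still severe at month 18 if followed, and let *s* be the share of them who have left. The ever-after-pairing figures are 2/110 = 1.8% and 8/110 = 7.3%. The month 18 figures are 2(1 − *s*)/82.5 and 8(1 − *s*)/82.5:

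| *s* | Month 18, 2 cases | Month 18, 8 cases |
|---|---|---|
| 0 | 2.4% | 9.7% |
| 0.25 | 1.8% | 7.3% |
| 0.50 | 1.2% | 4.8% |
| 0.75 | 0.6% | 2.4% |
| 1 | 0% | 0% |

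Dilution appears only when severe cases leave more often than the 25% overall. This is possible, since Protocol section XII lists safety and worsening health as reasons for termination, but it is not established.

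**4. What the safety route catches.** An event judged serious goes on an SAE form and into the by-arm tables. A non-serious event is recorded only if related or possibly related. The uncovered combination is therefore non-serious and unrelated, both judged with the arm known.

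**5. Baseline.** SAP 5.4 sets the C-SSRS baseline at the Home (Baseline) Visit, and SAP 6.3.6 reports suicidality at baseline. SAP Table 1 requires form 11 at Screening and Clearing Visit 1 and leaves Home/Baseline blank. Protocol Table 5 agrees with Table 1. As written, the baseline value does not exist.

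**The case against.** Several stronger readings are tempting, and the documents do not support them.

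- *The C-SSRS is reduced to one percentage per visit.* SAP 7.2.1 also plans a mixed model and a logistic regression, and a continuous score for thoughts of suicide could carry grade. What remains is that the score is undefined and that neither model reports behaviour separately.
- *The plan pools passive ideation with intent and behaviour.* No sentence says so. The term is undefined, and Hypothesis 2b concerns ideation. The supportable point is that nothing in the SAP prevents pooling.
- *An excess of severe suicidality in one arm would go unseen.* All SAEs are collected, including those judged unrelated. The SAE definition has a medical-judgment criterion that ideation needing intervention could meet without hospitalisation. SAEs are tabulated by arm, and the DMC reviews them and may ask for further tables. Protocol section XII adds a chart review for SAEs about 30 days after the withdrawal decision. This narrows the gap to the combination in step 4. One caveat: SAP 8 and Protocol section XIII each also say that only related or possibly related events must go on a study form. That sentence needs reconciling with the collection of all SAEs.
- *Veterans who leave disappear from the results.* A case recorded at a visit stays in that visit's figure, and Veterans may remain in follow-up after permanent removal of the dog.

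One objection bears on the remedy. The withdrawal procedures list no final C-SSRS, so a cumulative table built from form 11 alone would miss a Veteran who deteriorates between visits and is withdrawn. Keeping that Veteran in the denominator without comment would count them as event-free. This stands, and the fix allows for it.

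**Conclusion.** The point holds as a gap in definition and reporting. The SAP does not define suicidality or the thoughts-of-suicide score. It plans no by-arm view of severe ideation, behaviour or worsening across the post-pairing period, and it names a C-SSRS baseline that is not collected. Intent-level ideation or behaviour judged non-serious and unrelated reaches no safety table.

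The size cannot be stated, because it depends on severity rates and selective withdrawal that the documents do not give. The counts above are assumptions chosen to show the mechanism. A reader might want a power comparison between a severe category and a pooled flag, but any such figure would rest wholly on invented rates. Severe events are also likely to be too few for a formal test. Even zero events among 110 Veterans leaves an exact two-sided 95% upper limit of 1 − 0.025^(1/110) = 3.3%. With the fallback of 90 per arm it is 1 − 0.025^(1/90) = 4.0%.

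The primary analyses and the sample size do not depend on this. It is a cheap improvement to how harm is reported, and worth making before the final analysis.

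**What to change.** 1. In SAP 2.3.4 and 7.2.1, define the Hypothesis 2b outcome from the ideation items only, giving the items and the scoring. Report suicidal behaviour separately. State how the logistic regression handles repeated visits.
2. In SAP 8, add one descriptive by-arm table from form 11, cumulative to 18 months over all paired Veterans. It should show the worst post-pairing ideation grade (including any question 4 or 5), any suicidal behaviour, and worsening over the worst pre-pairing category, with exact intervals.
3. In the same table, include suicidal events found through SAE reports and the post-withdrawal chart review. Show the number in each arm withdrawn without a later C-SSRS, and do not count them as event-free.
4. Correct the C-SSRS baseline in SAP 5.4, and the matching summary in 6.3.6, to a visit at which Table 1 collects the form.

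The cost is SAP wording and one table from data already collected. There is no new visit or form. The downside is small counts, so the table stays descriptive. These changes concern analysis and reporting only; no clinical rule is proposed.

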### 7.2.2 To characterize and compare how health care utilization and costs are affected by the provision of a Service Dog or Emotional Support Dog.

The health care utilization and cost analyses will utilize VA databases, participant records and the Health Economics Research Center (HERC) developed non-VA utilization questionnaire. These analyses will be conducted by HERC. For a detailed description of the healthcare utilization and cost analyses, see the protocol.

### 7.2.3 To characterize and compare how employment and productivity are affected by the provision of a Service Dog or Emotional Support Dog

The employment and productivity analyses will utilize the WPAI: SHP V2.0 questionnaire and will be conducted by the Health Economics Research Center (HERC). For a detailed description of the healthcare utilization and cost analyses, see the protocol.

## 8 ADVERSE EVENTS

An Adverse Event (AE) can be any unfavorable or unintended sign (including an abnormal laboratory finding), symptom, or disease temporally associated with the study interventions. For the purposes of this study, the study interventions are 1) being paired with a Service Dog and 2) being paired with an Emotional Support Dog. In this study, information on AEs related to or possibly related to study intervention, for the participant, participant family members or the study dog, and on all serious adverse events (SAEs) will be collected and recorded.

Adverse events will be recorded during screening, observation phase and during the 18 months of follow-up. The reporting period for AEs begins when the participant signs the informed consent form and continues until the earlier of the 30 days after the participant's completion or early termination of study participation or the end of the study. All adverse events with a reasonable causal relationship to the study intervention should be considered "related". A definite relationship does not need to be established. The following levels of relatedness will be used in this trial:

- Not attributed to a study intervention (study dog)
- Possibly attributed to a study intervention (study dog)
- Attributed to a study intervention (study dog)

Only possibly related or related events must be reported on a study form.

Incidence of adverse events will be summarized for each treatment group by body system and MedDRA term. The number and percentage of participants with each body system and MedDRA term will be presented for each treatment group. Tables to summarize the incidence rates will be created for each of the following groups:

- Adverse events
- Adverse events by relationship to treatment
- Adverse events leading to premature discontinuation
- Adverse events presented in descending order of frequency by MedDRA term (no System Organ Class shown)
- Serious adverse events
- Serious adverse events by type
- Serious adverse events by relationship to treatment

Adverse events that led to premature discontinuation from the study will be listed. Serious adverse events will also be listed. These listings will contain details about the adverse event such as intensity and relationship to study treatment. All adverse events will be coded with MedDRA (updated version).

## **9 STATISTICAL PROGRAM VALIDATION PLAN**

Perry Point Work Instruction (WI) 202 – Validation Plan for SAS Statistical Programs will serve as the validation plan for validation of the statistical programs created for the analyses of data collected during this study.

**APPENDIX 1: TABLES****TABLE 3: Number of Participants Entered and Number Expected**

Site	Number Consented	Number Randomized	Number Expected	Percent of Expected
Atlanta				
Iowa City				
Portland				
Total				

**TABLE 4: Participants Screened/Randomized by Month**

Site	Month 1		Month 2		Month 3		Total	
	Screened	Randomized	Screened	Randomized	Screened	Randomized	Screened	Randomized
Atlanta								
Iowa City								
Portland								
TOTAL								

**FIGURE 1: Observed Versus Expected Participant Recruitment****TABLE 5: Cumulative Screening Summary: All Participants by Site**

Site	Status of Consented Participants				Status of Randomized Participants	
	Consented	Screen Failure	In Screening	Randomized	In obs. Phase	Paired
Atlanta						
Iowa City						
Portland						
Total						

**TABLE 6: Summary of Ineligibility: Reasons for Exclusion, Total and Site**

TOTAL NUMBER SCREENED = \_\_\_\_\_

Reason	No. Excluded	% of Screened
Less than 18 years of age		
No Referral from Mental Health provider, which documents PTSD diagnosis.		
Does not have PTSD as a result of a trauma by meeting DSM 5 criteria		
Not Enrolled in mental health at VA or has not attended at least one visit in the past 90 days prior to consent.		
Does not agree to remain in mental health therapy throughout the duration of the study.		
Cannot adequately care for a dog.		
Home environment is not suitable for a dog		
Home environment is not accessible for study staff.		
Does not have anyone to care for dog in the long-term absence of Veteran		
Others in home do not agree to have a dog		
Not willing and/or able to travel (by air or car) to training site for pairing		
Subject has cats, dogs or other household pets in home		
Not able to verbalize understanding of consent form or provide written informed consent		
Was hospitalized in the past 6 months for mental health reasons		
Participant has aggressive behavior what would make it unsafe for dog		
Diagnosis of psychoses, delusions, dementia, active alcohol/substance dependence or moderate to server TBI.		

Active suicidal intent as determined by a CPRS flag for suicidal intent or a score $\geq 5$ on the C-SSRS completed at the baseline visit.		
Homicidal intent or cognitive disabilities that would preclude safety of dog and/or ability to participate in study.		
Social, mental or physical condition that prevents participant from giving informed consent		
Participation in another research trial		
Has chart note flag for violent/disruptive behavior		
Has children younger than age 10 in the household for more than 8 hours per day, on day a week or more.		

**TABLE 7. Participant Disposition**

Site	Consented	In Screening	Randomized	In Observation Phase	Waiting for Clearing Visit	Waiting for Pairing	Emotional Support Dog	Service Dog	Completed Study
Atlanta									
Iowa City									
Portland									
TOTAL									

**TABLE 8: Demographic Variables by Site**

Variables	Participating Site				p-value
	1	2	3	TOTAL	
Age (Mean(SD))					
Gender (N (%))					
Male					
Female					
Ethnicity (N (%))					
Asian-American					
African-American					
Caucasian					
Hispanic					
Native-American					
Other					
Marital Status (N (%))					
Married					
Divorced					
Civil Commitment					
Never Married					
Co-habiting					
Separated					
Widowed					
Income (N (%))					
< \$10,000					
\$10,001 - \$20,000					
\$20,001 - \$30,000					
\$30,001 - \$40,000					
\$40,001 - \$50,000					
\$50,001 - \$60,000					
\$60,001 - \$70,000					
> \$70,001					

**TABLE 9. Baseline, Observational Phase and Clearing Visit WHODAS 2.0 Scores**

	Baseline Mean $\pm$ SD	Clearing Visit Mean $\pm$ SD
Understanding & Communicating		
Mobility		
Self-Care		
Getting along with Others		
Life Activities		
Participation in Society		
Summary Score		

**TABLE 10. WHODAS 2.0 Scores by Treatment Group**

	3 month Mean $\pm$ SD	6 month Mean $\pm$ SD	9 month Mean $\pm$ SD	12 month Mean $\pm$ SD	15 month Mean $\pm$ SD	18 month Mean $\pm$ SD
	SERV	EMOT	SERV	EMOT	SERV	EMOT
Understanding & Communicating						
Mobility						
Self-Care						
Getting along with Others						
Life Activities						
Participation in Society						
Summary Score						

**TABLE 11. Baseline, Observational Phase and Clearing Visit VR-12 Scores**

	Baseline Mean $\pm$ SD	Clearing Visit Mean $\pm$ SD
MCS		
PCS		

**TABLE 12. VR-12 Scores by Treatment Group**

	3 month Mean $\pm$ SD	6 month Mean $\pm$ SD	9 month Mean $\pm$ SD	12 month Mean $\pm$ SD	15 month Mean $\pm$ SD	18 month Mean $\pm$ SD				
	SERV	EMOT	SERV	EMOT	SERV	EMOT	SERV	EMOT	SERV	EMOT
MCS										
PCS										

